9.2.2 Assessment of secondary outcomes

- To evaluate whether pathological changes seen in SD-OCT or color fundus photography correlate with changes seen in High-Res-OCT, a binary readout will be used, i.e. pathology present yes/no.
- Subgroup analysis will be performed with patients suffering from diabetic retinopathy, artery and vein occlusion, retinal detachment, glaucoma, optic nerve neuropathy, hereditary retinal diseases, age related macular degeneration, retinal changes from arterial hypertension and uveitis. For this purpose a quantification and classification of the pathological changes in relation to each disease will be performed, among them; Drusen classification according to Age-Related Eye Disease Study (AREDS) ²⁷, neovascularization, bleeding, ischemia, atrophy, exudate, retinal thickness, intra-subretinal fluid, pigment epithelial detachment (PED) and epiretinal membrane ^{28,29}. In order to compare these groups with conventional imaging and controlling for some degree of variation due to age, patients included in subgroup analysis will be compared to a pool of healthy subjects.
- Evaluation of the intra- and inter-reader reproducibility in the diagnosis using High-Res-OCT. This will result in a binary outcome (diagnosis present or absent). The evaluation of the inter-reader reproducibility in healthy subjects with High-Res-OCT will be assessed. For this purpose a senior physician, a resident and an expert physician will subsequently analyze the images.
- Furthermore the quality of the segmentation of the retinal layers, i.e. the discrimination capacity between the different layers (internal limiting membrane, retinal nerve fibre layer, ganglion cell layer, inner plexiform layer, inner nuclear layer, outer plexiform layer, outer nuclear layer, external limiting membrane, photoreceptor layer, retinal pigment epithelium, Bruch's membrane, choriocapillaris and choroidal stroma) will be assessed, especially in the healthy group. For this purpose, a binary outcome will also result, i.e. discrimination between each layer possible, yes or no.

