6. CLINICAL INVESTIGATION DESIGN

6.1 General clinical investigation design and justification of design

This trial is a prospective clinical study. Patients, who fulfilled the inclusion criteria will be recruited at the Inselspital Bern. Study data will be collected in REDCap®, a secure, and validated web application for building and managing online surveys and databases. Study participants will undergo imaging of one or both eyes in accordance with the clinical indication, which will last approximately 30-60 seconds per eye. The imaging process is without any contact and pharmacologic dilatation of the pupils will not be used for the purposes of this study.

We plan to include approximately 550 participants in the study, including 100 healthy participants and 450 patients with diagnosed ocular disorders, including diabetic retinopathy (50 patients), artery and vein occlusion (50 patients), glaucoma (50 patients), optic nerve neuropathy (50 patients), hereditary retinal diseases/dystrophies (50 patients), retinal detachment (50 patients), age related macular degeneration (50 patients), retinal changes from arterial hypertension (50 patients), uveitis (50 patients).

Study participants will undergo imaging with High-Resolution OCT only within a single imaging session on a single day. Additionally, study participants will be asked to consent to prospective collection of clinical and demographic data, to correlate findings of High-Resolution OCT imaging to subsequent clinical course. Data from the clinical records are to be used for the study up to the time of the visit.

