7. CLINICAL INVESTIGATION POPULATION

7.1 Eligibility criteria

Subjects fulfilling all of the following inclusion criteria are eligible for the investigation:

- Informed Consent signed by the subject
 - Patients and healthy subjects from the Department of Ophthalmology, University Hospital Bern requiring conventional imaging for eye disease
 - Patients of 18 years or older

The presence of any one of the following exclusion criteria will lead to the exclusion of the subject

- Patients not willing or able to sign informed consent
- Patients younger than 18 years
- Contraindication and limitation of the MD as described in the instructions for use: Patients with epilepsy.
- Vulnerable subjects (except the objectives of the investigation concern vulnerable subjects specifically),
- Inability to follow the procedures of the investigation, e.g. due to language problems, psychological disorders, dementia, etc. of the subject
- Participation in another investigation with an investigational drug or another MD within the 30 days preceding and during the present investigation
- Enrolment of the PI, his/her family members, employees and other dependent persons

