7.2 Recruitment and screening

There will be a consecutive ongoing recruitment of patients and healthy subjects attending routine follow-ups through the involved investigators in daily clinical practice at Department of Ophthalmology, Inselspital, Bern. Recruitment will last from October 2021 to November 2023. Subjects will be given enough time (hours to days) to consider and to council with relatives and experts. No screening requirements is necessary (laboratory or other diagnostic tests). There will be no payment or compensation given to subjects.

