7.3 Assignment to investigation groups

The recruited participants will be assigned to the diagnostic categories mentioned at 6.1. or categorized as healthy. No randomization is planned.

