11.4.3 Secondary Analyses

Subgroup analysis will be performed to differentiate different disease entities using non-parametric test with a significance level of 0.05, with patients suffering from diabetic retinopathy, glaucoma, optic nerve neuropathy, hereditary retinal diseases, retinal detachment, artery and vein occlusion, age related macular degeneration, retinal changes from arterial hypertension and uveitis. In order to compare these groups with conventional imaging and controlling for some degree of variation due to age, we estimate a group size of approximately 50 patients and 100 healthy subjects ¹⁶.

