12.1.2 Specification of source data and source documents

Source data will be available at the site to document the existence of the investigation subjects. Source data will include the original documents relating to the investigation, as well as the medical treatment and medical history of the subject.

The source documents include:

- Demographic form: Study ID, study eye, personal information (year of birth, age, sex), eye anamnesis (diagnosis, date of diagnosis, recurrences). Data will be entered electronically in REDcap.
- Examination form (data from both eyes): visit date and if applicable, visual acuity, SD-OCT; FA, ICG, FAF plus additional information if required (correction). Data will be entered electronically in REDcap.
- Informed consent form; stored in a locked cupboard.

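### In the secondary patient-versus-healthy comparisons, neither the healthy pool nor the group sizes control for age; age should be adjusted for in a stated model

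*Combined protocol and SAP*

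**What the plan says.** Section 9.2.2 plans to quantify and classify findings by disease, including drusen grade, atrophy, fluid and retinal thickness. It then states that, "controlling for some degree of variation due to age, patients included in subgroup analysis will be compared to a pool of healthy subjects". Section 11.4.3 links age to numbers instead: "controlling for some degree of variation due to age, we estimate a group size of approximately 50 patients and 100 healthy subjects". The synopsis repeats that wording under the number of subjects and under statistical considerations.

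The sample is described as "including 100 healthy participants and 450 patients with diagnosed ocular disorders" (section 6.1), so one healthy group serves nine disease groups of 50. Section 7.2 plans "consecutive ongoing recruitment of patients and healthy subjects attending routine follow-ups". The only age criterion in section 7.1 is "Patients of 18 years or older". On grouping, section 7.3 says: "The recruited participants will be assigned to the diagnostic categories mentioned at 6.1. or categorized as healthy".

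The subgroup analysis in section 11.4.3 is to be done "using non-parametric test with a significance level of 0.05", with no test or covariate named. Section 12.1.2 records "personal information (year of birth, age, sex" on the demographic form. Section 11.4.1 uses age only descriptively, by group. The synopsis also lists age-dependent changes as a secondary endpoint, without a method.

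**The concern.** A comparison group controls for age only if its ages are made similar to those of the patients, or if age enters the analysis. Pooling healthy volunteers does neither. A larger group reduces random error but leaves a systematic age difference untouched. Nine diagnoses that include hereditary disease and age-related macular degeneration cannot all be assumed to share the age profile of one healthy pool.

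If a graded or incidental finding, or retinal thickness, varies with age, an age gap will show up as a difference between patients and healthy subjects. A report that follows the plan could then describe age as partly controlled when nothing had been done about it.

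**Working it through.** **1. The plan's own figures.** 9 × 50 + 100 = 550, which agrees with the stated total. The sizes of 50 and 100 cannot be reproduced, because no effect size, power, variance or age distribution is given for the subgroup comparison. At 80% power and two-sided 0.05 they would detect about 18.5 percentage points from a 10% rate, or 23.5 points from 50%, before any allowance for age.

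**2. Is age controlled anywhere else?**
- Design: not randomised (6.2, 6.2.1), and other methods for minimising bias are marked not applicable (6.2.3).
- Recruitment: consecutive, with no age quota or stratum (7.2), and a lower age limit only (7.1).
- Grouping: by diagnosis or healthy status (7.3).
- Analysis: a non-parametric test at 0.05 (11.4, 11.4.3), with age only described (11.4.1).

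None of these balances or adjusts for age.

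**3. Size of the effect, on assumed inputs.** From the plan: 50 patients, 100 healthy subjects, level 0.05. Assumed: age SD 12 years in each group, within-group outcome-age correlation r of 0.2 or 0.3, a linear age effect, no true group effect, and an unadjusted two-sided rank test.

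- Shift caused by age, in outcome SDs: δ = r × gap / 12.
- SE = √(1/50 + 1/100) = 0.173.
- For a rank test, z = √(3/π) × δ / SE = 0.977 × δ / 0.173.
- Rejection rate ≈ Φ(z − 1.96) + Φ(−z − 1.96).

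| r | Age gap (years) | δ | z | Formula | Simulation (4,000 trials) |
|---|---|---|---|---|---|
| 0.2 | 5 | 0.083 | 0.47 | 7.6% | 7.3% |
| 0.2 | 10 | 0.167 | 0.94 | 15.6% | 15.4% |
| 0.2 | 20 | 0.333 | 1.88 | 46.8% | 46.0% |
| 0.3 | 5 | 0.125 | 0.71 | 10.9% | 10.3% |
| 0.3 | 10 | 0.250 | 1.41 | 29.2% | 28.6% |
| 0.3 | 20 | 0.500 | 2.82 | 80.5% | 79.6% |

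Linear regression on group and age rejected in 4.5-5.3% of the same trials. With no age gap the unadjusted test keeps its 5% level, but nothing in the plan secures that.

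**4. Binary findings.** Assume 20% prevalence at age 50 and an odds ratio of 1.5 to 2.0 per 10 years. The unadjusted comparison rejects in 9-13%, 18-37% and 53-92% of trials at gaps of 5, 10 and 20 years. Logistic regression with age gives 4-5%.

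**5. Does group size help?** Four times the numbers (200 versus 400) halves the SE to 0.087. At a 10-year gap z doubles to 1.88 or 2.82, so the rejection rate rises from about 16% or 29% to about 47% or 80%. Larger groups make the false finding more likely.

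**6. Cost of adjusting.** Variance inflation is 1 + (1/3)(2/3) × gap² / 144. At gaps of 5, 10 and 20 years this is 1.04, 1.15 and 1.62, so 50 patients carry the information of about 48, 43 and 31.

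**7. Limits of simple adjustment.**
- If the age effect starts only at 60 (assumed 0.5-0.8 SD per decade after that), linear adjustment rejects from about 7% upwards at a 20-year gap and in about 11-18% of trials at 25 years.
- If a finding has a true rate of 0.5%, 1% or 2% in healthy subjects, the chance of no event among 100 is 0.995^100 = 61%, 0.99^100 = 37% or 0.98^100 = 13%. Ordinary logistic regression then breaks down.

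**The case against.** The plan claims control of only some degree of age variation, and it lists age-dependent changes as a topic of study. That softens the claim, but the means described still provide no control, and the age endpoint has no method.

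Three stronger readings are tempting, and the documents do not support them:

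- **That age confounds the comparison of High-Res-OCT with conventional imaging.** The sentence in 9.2.2 mentions that comparison, so a reader might infer this. But the comparison is made within the same subject (9.1, 9.3), so a difference in age between groups cannot confound it. The primary outcome is unaffected.
- **That the plan prescribes an unadjusted two-group test.** It names no test. Section 11.4.3 speaks of differentiating disease entities, which could mean a comparison across disease groups. The rank test above is an assumption used to show the scale.
- **That the pool is declared unmatched.** The documents are silent. The absence of matching is inferred from consecutive recruitment, a lower age limit only and grouping by diagnosis.

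It is also fair to say that an absence of any true group effect makes no sense for a feature that defines the group, such as drusen in macular degeneration. The error rates apply to incidental or graded features and to thickness. The age gaps, SD and correlations are not anchored in any document.

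**Conclusion.** The point holds for the secondary patient-versus-healthy comparisons. The plan credits the healthy pool and the group sizes with some control of age, and neither can deliver it. This is more than a missing detail, because the stated means cannot produce the stated property.

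That conclusion rests on the text and is firm. The magnitude is illustrative: at an assumed 10-year gap, roughly 15-29% false rejections for a continuous outcome instead of 5%. It depends on an age gap and an age effect that the documents do not give. The matter should be corrected before analysis, but it does not threaten the primary result.

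**What to change.** In 9.2.2 and 11.4.3, state that each patient-versus-healthy outcome is analysed by regression on disease group and age:

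- **Binary findings:** logistic regression, penalised or exact where healthy subjects have few or no events.
- **Graded findings:** ordinal regression.
- **Retinal thickness:** linear or rank-based analysis of covariance.
- **Age term:** allow it to be non-linear.
- **Eyes:** use one study eye per subject, or account for two eyes. Section 6.1 allows one or both eyes to be imaged, and the form in 12.1.2 holds data from both.
- **Overlap:** report the age overlap of each disease group with the healthy pool, and restrict or label as descriptive any comparison with little overlap.

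Delete the statement that the pool or the group size controls for age in 9.2.2, in 11.4.3 and in both places in the synopsis.

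The cost is wording and analysis time. Age and study eye are already on the demographic form, and no new visits or subjects are needed. The statistical price is the modest loss of precision shown above, and dependence on the model where age overlap is thin.

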4.3 Secondary Objectives

- Evaluation of the inter-reader reproducibility in healthy subjects with High-Res-OCT
- Evaluation whether pathological changes seen in SD-OCT or color fundus photography correlate with changes seen in High-Res-OCT. Here, a binary readout, i.e pathology present (yes/no) will be used.
- Subgroup analysis will be performed with patients suffering from diabetic retinopathy, artery and vein occlusion, retinal detachment, glaucoma, optic nerve neuropathy, hereditary retinal diseases, age related macular degeneration, retinal changes from arterial hypertension and uveitis.
- Evaluation of the intra-and inter-reader reproducibility in the diagnosis (binary) using High-Res-OCT
- Evaluation of the segmentation quality of the retinal layers using High-Res-OCT

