9.2.1 Assessment of primary outcome

The sensitivity and specificity of the High-Resolution OCT to diagnose the presence/absence of pathological changes in the retina/optic nerve in comparison to conventional imaging modalities will be assessed as a primary outcome. The following pathological changes will be assessed: intraretinal or subretinal fluid, pigment epithelial detachment, epiretinal membrane, substance defect, drusen, hyperreflective foci, atrophy, neovascularization, choroid abnormalities, scars, optic nerve swelling and ischemia. For each of these pathological changes a binary outcome will result. Additionally, study participants will be asked to consent to prospective collection of clinical and demographic data, to correlate findings of High-Res-OCT imaging to subsequent clinical course.

There is no need to be in a particular posture before the examination in order to obtain high quality images. The participants will be in a sitting position during the examination during approximately 30-60 seconds per eye. In case the measurement needs to be repeated, no waiting period will be necessary. A repeated measurement needs to be recorded in the CRF.

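### Reader reproducibility of the diagnosis is scored as a single present/absent outcome, which on its plainer reading cannot show whether readers agree on the disease

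*Combined protocol and SAP*

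**What the plan says.** The secondary objective in 4.3 is "Evaluation of the intra-and inter-reader reproducibility in the diagnosis (binary) using High-Res-OCT"; the synopsis and 5.2 carry the same binary label. Section 9.2.2 restates it as "Evaluation of the intra- and inter-reader reproducibility in the diagnosis using High-Res-OCT" and then fixes the scale: "This will result in a binary outcome (diagnosis present or absent"). Three readers are named: "a senior physician, a resident and an expert physician will subsequently analyze the images". The healthy group has its own inter-reader outcome: "The evaluation of the inter-reader reproducibility in healthy subjects with High-Res-OCT will be assessed".

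Section 6.1 sets the case mix, "including 100 healthy participants and 450 patients with diagnosed ocular disorders", with the patients divided into nine disease groups of 50. Section 7.3 uses those groups as the study's labels: "The recruited participants will be assigned to the diagnostic categories mentioned at 6.1. or categorized as healthy".

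For the primary outcome, 9.2.1 scores item by item: "For each of these pathological changes a binary outcome will result". The layer-segmentation outcome in 9.2.2 and the exploratory outcome in 9.2.3 are also scored item by item. The reader outcome has no such wording. Section 11 names no agreement statistic for reader reproducibility.

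**The concern.** The outcome is described as reproducibility of the diagnosis, and the study distinguishes nine diseases. A single present/absent score discards which disease the reader saw. If one reader calls glaucoma and another optic nerve neuropathy, both readings are present and the pair agrees. The same happens when one reader changes from age-related macular degeneration to hereditary disease on a second read.

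About 82% of participants (450 of 550) are enrolled with a disease, so this affects most of the data. The overall aim in 4.1 is whether the device can reliably diagnose retinopathies. This outcome is the plan's direct evidence on reliability between and within readers. On the any-diagnosis reading it shows only that readers agree something is abnormal.

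**Working it through.** The plan gives no target, precision or expected value for reader agreement, so there is no stated figure to reproduce. The check is to score the same readings in different ways.

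**What needs no assumption.** If two readings carry the same label (the same disease, or both none), they also match on present/absent. The converse is false. Percent agreement on present/absent is therefore never below percent agreement on the named label.

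**Inputs from the plan.** 100 healthy and 9 × 50 diseased, 550 in total (6.1); ten labels (7.3).

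**Assumptions, not in the documents.** Two readers independent given the true label; detection s = 0.95; false positives f = 0.10; correct disease named with probability c once something is detected; wrong names spread evenly (over the 8 other diseases for patients, over 9 for healthy subjects).

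**Present/absent agreement.**
- Diseased: s² + (1−s)² = 0.9025 + 0.0025 = 0.905. Healthy: f² + (1−f)² = 0.01 + 0.81 = 0.82.
- Overall: (450 × 0.905 + 100 × 0.82)/550 = 489.25/550 = 0.890.
- Marginal present rate: (427.5 + 10)/550 = 0.7955. Chance agreement: 0.7955² + 0.2045² = 0.6746.
- Kappa: (0.8895 − 0.6746)/(1 − 0.6746) = 0.66. The accuracy c does not enter.

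**Named-disease agreement, c = 0.9.**
- Diseased: s²[c² + (1−c)²/8] + (1−s)² = 0.9025 × 0.81125 + 0.0025 = 0.7347. Healthy: 0.81 + 0.01/9 = 0.8111.
- Overall: (450 × 0.7347 + 100 × 0.8111)/550 = 0.749.
- Chance agreement: 0.2045² + 9 × (0.7955/9)² = 0.0418 + 0.0703 = 0.1121.
- Kappa: (0.7486 − 0.1121)/(1 − 0.1121) = 0.72.

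| Correct naming c | Present/absent: agreement, kappa | Named disease: agreement, kappa | Both-present pairs naming different diseases |
|---|---|---|---|
| 0.9 | 0.890, 0.661 | 0.749, 0.717 | 19% |
| 0.8 | 0.890, 0.661 | 0.626, 0.579 | 36% |
| 0.7 | 0.890, 0.661 | 0.520, 0.459 | 50% |
| 0.6 | 0.890, 0.661 | 0.430, 0.358 | 62% |

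The two kappas cross at c of about 0.86.

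**Other reader performance.** With detection and specificity both 0.90, present/absent gives 0.820 and kappa 0.514. Named-disease scoring gives 0.693 and 0.650 at c = 0.9, 0.583 and 0.524 at c = 0.8, and 0.488 and 0.416 at c = 0.7. With detection 0.98 and specificity 0.95, present/absent gives 0.951 and 0.839, against 0.802 and 0.778 for the named disease at c = 0.9. Percent agreement keeps the same order throughout; kappa does not.

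**If the outcome is read as one yes/no per disease** (s = 0.95, f = 0.10, c = 0.9). Both readers call a given disease with probability [50 × 0.855² + 400 × (0.095/8)² + 100 × (0.1/9)²]/550 = 0.0666. Each reader calls it with probability 0.7955/9 = 0.0884. Agreement is 1 − 2 × (0.0884 − 0.0666) = 0.956. Chance agreement is 0.0884² + 0.9116² = 0.8389, so kappa is (0.9564 − 0.8389)/(1 − 0.8389) = 0.73. Different names now count as disagreement, but percent agreement is high because each disease is absent in 500 of 550 subjects (91%).

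**The case against.** The strongest reply is that the plan nowhere says readers naming different diseases count as agreeing. That follows only from the any-diagnosis reading. The plan uses binary in an item-by-item sense elsewhere, and present or absent could refer to a given diagnosis. This stands as an ambiguity: the per-disease reading is not excluded. It is the less natural one, because the sentence describes one outcome and omits the per-item wording found in 9.2.1, in the segmentation item of 9.2.2 and in 9.2.3. If it was intended, 9.2.2 still needs to say so.

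A reader might also infer that reported reproducibility will be too high. The documents do not support that in general. They name no statistic, and the direction is fixed only for percent agreement under the any-diagnosis reading. At 90% correct naming, the present/absent kappa (0.66) is below the named-disease kappa (0.72).

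The plan also uses diagnose for detecting morphological abnormalities (4.2, 9.2.1), so binary agreement has a legitimate use, most clearly in the healthy group. That supports keeping it, but not as the only measure in a study with nine disease groups.

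Finally, a forced choice among ten labels could not record coexisting disease or a disease outside the list, and 5.1 says its list is not exhaustive. The fix allows for both. The CRF is a separate appendix, so whether readers already record the disease cannot be checked.

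**Conclusion.** The concern holds in limited form. On the plainer reading of 9.2.2, agreement on which disease is present is not measured, and present/absent percent agreement is an upper bound on it. Under the assumed 95% detection, 10% false positives and 90% correct naming, the gap is about 14 percentage points (89% against 75%). It reaches 46 points (89% against 43%) only if naming accuracy is as low as 60%. These sizes rest on assumed reader performance, conditional independence and evenly spread wrong names; the documents give nothing to anchor them. No direction can be claimed for kappa. The outcome is secondary, has no target or decision rule, and does not bear on the primary comparison. It is still worth correcting before reading begins: present/absent can be derived from a recorded disease, but the disease cannot be recovered from a present/absent score without reading again.

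**What to change.** In 9.2.2, and correspondingly in the synopsis, 4.3 and 5.2, have each reader record present or absent for each of the nine diseases in 6.1. Allow more than one, add options for other disease and for healthy, and have the reader mark the main diagnosis. Define the reproducibility outcome as kappa with 95% CI for each disease, plus agreement on the main named diagnosis (multi-category kappa with 95% CI), both within and between readers. Keep any-diagnosis present/absent as a supplementary result. Name these statistics in 11.4.3.

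The cost is an added reader field, if the form does not already have it, and a little more analysis. The readers and images are the same. Reported percent agreement may be lower than under a single present/absent score.

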5.2 Secondary Outcomes

- Evaluation of the inter-reader reproducibility in healthy subjects with High-Res-OCT
- Evaluation whether pathological changes seen in SD-OCT or color fundus photography correlate with changes seen in High-Res-OCT. Here, a binary readout, i.e pathology present (yes/no) will be used.
- Subgroup analysis will be performed with patients suffering from diabetic retinopathy, artery and vein occlusion, retinal detachment, glaucoma, optic nerve neuropathy, hereditary retinal diseases, age related macular degeneration, retinal changes from arterial hypertension and uveitis
- Evaluation of the intra-and inter-reader reproducibility in the diagnosis (binary) using High-Res-OCT
- Evaluation of the segmentation quality of the retinal layers using High-Res-OCT. For this purpose the discrimination capacity between the different retinal layers will be assessed, especially in the healthy group. For this purpose, a binary outcome will also result.

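### Intra-reader reproducibility is a secondary outcome, but no second reading by the same reader is specified and no rule keeps the readers' calls independent

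*Combined protocol and SAP*

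**What the plan says.** The Synopsis and sections 4.3, 5.2 and 9.2.2 all promise reader reproducibility. Section 5.2 has two separate entries: "Evaluation of the inter-reader reproducibility in healthy subjects with High-Res-OCT" and, with no limit on population, "Evaluation of the intra-and inter-reader reproducibility in the diagnosis (binary) using High-Res-OCT". Section 9.2.2 puts both into one bullet. It opens with "Evaluation of the intra- and inter-reader reproducibility in the diagnosis using High-Res-OCT", says that the readout is diagnosis present or absent, then adds "The evaluation of the inter-reader reproducibility in healthy subjects with High-Res-OCT will be assessed", and ends with the only description of the reading itself: "For this purpose a senior physician, a resident and an expert physician will subsequently analyze the images".

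Section 6.2 calls the study open label. Sections 6.2.2 (blinding) and 6.2.3 (other bias control) are both marked as not applicable. Under section 7.3 each participant is assigned to a diagnostic category or to the healthy group.

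Section 6.1 gives the numbers available: "including 100 healthy participants and 450 patients with diagnosed ocular disorders". It allows one or both eyes to be imaged. Section 11 names no agreement statistic and sets no precision target for reproducibility.

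**The concern.** Intra-reader reproducibility compares a reader with himself or herself, so it needs at least two readings of the same image by the same person. The plan names the outcome but provides for only one pass by three people. A team that follows it exactly will reach the end of the study with nothing to analyse for that outcome.

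Inter-reader agreement can be estimated from three readers, but it reflects reproducibility only if each call is made without knowledge of the others and of the diagnosis already on file. The plan has no such rule, and its bias-control sections are closed as not applicable. An agreement figure obtained this way could partly reflect shared information.

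The image set and the statistic are also left open, so both could be chosen after the readings are seen. For the healthy-only outcome the choice matters, because a chance-corrected measure behaves badly when few subjects have a finding.

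**Working it through.** The plan states no figure for reproducibility, so there is none to reproduce. The check has three parts.

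**1. Which pairs does the scheme yield?** With R readers and m readings each, an image gives R(R − 1)/2 between-reader pairs on the first readings and R × m(m − 1)/2 within-reader pairs. Section 9.2.2 gives R = 3 and describes one analysis of the images, so m = 1.

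- Between readers: 3 × 2/2 = 3 pairs per image.
- Within readers: 3 × (1 × 0)/2 = 0 pairs per image.

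Other sections do not supply the second reading. The repeated measurement in 9.2.1 is a repeat image acquisition. Sections 8.3 and 9.3 say that examination or imaging happens once and do not address reading. Section 12.1.1 names two case report forms, for demographics and clinical examination, and the form contents in 12.1.2 include no field for a reader or a repeat reading.

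**2. Which way does a lack of independence act?** Suppose that two readers have equal rates of positive calls, and that the second adopts the first's call in a share c of images. Observed agreement rises from p_o to c + (1 − c)p_o, while chance agreement p_e is unchanged. Kappa therefore rises from κ to κ + c(1 − κ). For any c above 0 the shift is upward. The documents say nothing about c, so the size cannot be given.

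**3. How does kappa behave in the healthy group?** Inputs from section 6.1 are 100 healthy participants and 450 patients. Assumed inputs are reader sensitivity 0.90, reader specificity 0.95, errors independent given the truth, and a healthy-group prevalence π of findings from 0% to 20%. For the full set, all 450 patients and none of the healthy are taken to have a finding.

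- p_o = π[se² + (1 − se)²] + (1 − π)[sp² + (1 − sp)²]
- p = π·se + (1 − π)(1 − sp)
- p_e = p² + (1 − p)²
- κ = (p_o − p_e)/(1 − p_e)

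Example at π = 0.02: p_o = 0.02 × 0.82 + 0.98 × 0.905 = 0.903; p = 0.018 + 0.049 = 0.067; p_e = 0.0045 + 0.8705 = 0.875; κ = 0.0283/0.125 = 0.23.

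| Set | Prevalence | Agreement | Kappa | 95% sampling range |
|---|---|---|---|---|
| Healthy, N = 100 | 0% | 0.905 | 0.00 | −0.08 to 0.26 |
| Healthy, N = 100 | 2% | 0.903 | 0.23 | −0.06 to 0.56 |
| Healthy, N = 100 | 5% | 0.901 | 0.41 | 0.08 to 0.69 |
| Healthy, N = 100 | 10% | 0.897 | 0.56 | 0.29 to 0.78 |
| Healthy, N = 100 | 20% | 0.888 | 0.67 | 0.48 to 0.83 |
| All, N = 550 | 450/550 | 0.835 | 0.57 | 0.48 to 0.64 |

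The ranges come from 5,000 simulated data sets per row. With specificity between 0.90 and 0.98, kappa at 2% prevalence runs from 0.12 to 0.42. Reader skill is the same in every row of the table. In the healthy rows percent agreement hardly moves, while kappa goes from 0 to 0.67 with prevalence alone.

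**The case against.** The best defence is that the protocol is silent here and says nothing wrong. It gives no number of readings, the images are stored, and re-reading them needs no new participant procedure. That is fair as far as it goes. A reader might infer that no reader will read twice and that the outcome cannot be delivered. The documents support only that no second reading is specified, and the gap can be closed at any time before analysis.

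A reader might also infer that the physicians read in sequence and see each other's results. The word *subsequently* may mean no more than afterwards, and reading in turn is not a fault in itself. What stands is that independence is not required anywhere and that the blinding section rules nothing in.

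A third tempting inference is that only healthy images are read, that almost none are positive, and that kappa is therefore 0. The reader sentence does follow the healthy-subject sentence, but its opening words can equally refer to the whole bullet, and sections 4.3 and 5.2 list the general outcome without that limit. No prevalence is given and healthy is not defined. Section 7.1 even admits "Patients and healthy subjects from the Department of Ophthalmology, University Hospital Bern requiring conventional imaging for eye disease". Kappa of 0 needs exactly no true findings together with independent errors, and the plan never names kappa. Simple agreement on absence in healthy subjects remains a legitimate check on consistency of false positives.

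None of this supplies within-reader data or a masking rule.

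**Conclusion.** The concern holds in a limited form. Intra-reader reproducibility is promised in four places and, as the scheme is written, rests on 0 within-reader pairs. This follows from the text and needs no assumption beyond taking the single described analysis as one reading.

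Inter-reader agreement is estimable, but it is unprotected against knowledge of other calls or of the diagnosis. The bias would be upward and its size is unknown.

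The instability of kappa in healthy subjects is conditional. It rests on assumed reader accuracy and on a prevalence that the documents do not give. It is a reason to report the healthy group separately and descriptively, and it does not show that the healthy-only outcome is empty.

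The point is confined to secondary outcomes and is a worthwhile improvement of modest weight.

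**What to change.** In sections 9.2.2 and 6.2.2, state the following.

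- The same three physicians read the High-Res-OCT images independently, masked to each other's calls and to the diagnostic group.
- Each re-reads a random subset stratified by diagnosis, in new order and after a fixed interval. For example, 10 from each of the 9 disease groups plus 20 healthy: 9 × 10 + 20 = 110 participants.
- Inter- and intra-reader kappa, with positive and negative agreement, are reported on the mixed diseased and healthy set. Healthy-only inter-reader agreement is a separate descriptive outcome.
- Section 11 names these statistics, the image set, the unit (eye or participant) and the precision aimed for.

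The example subset keeps the case mix of the whole study, since 90/110 = 450/550. As a rough guide under the assumptions above, the range for kappa would widen from 0.16 at 550 to about 0.16 × √(550/110) = 0.36 at 110. The sponsor should judge whether that is enough.

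Cost: about 110 extra participant-readings for each existing reader. If only healthy images were meant to be read the first time, the 90 patients need two readings and the 20 healthy one more: 2 × 90 + 20 = 200 per reader. Reading both eyes would up to double either figure. No new reader, visit or participant procedure is needed.
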